6.3 STUDY INTERVENTION COMPLIANCE

Compliance to the protocol will be monitored using software for the VR modules and remote data uploads of survey logs.

6.4 CONCOMITANT THERAPY

For this protocol, a prescription medication is defined as a medication that can be prescribed only by a properly authorized/licensed clinician. Medications to be recorded are concomitant prescription medications, over-the-counter medications, and supplements.

7 STUDY INTERVENTION DISCONTINUATION AND PARTICIPANT DISCONTINUATION/WITHDRAWAL

7.1 DISCONTINUATION OF STUDY INTERVENTION

Discontinuation from the use of the digital pain reduction kit does not mean discontinuation from the study, and remaining study procedures should be completed as indicated by the study protocol. If a clinically significant finding is identified (including, but not limited to changes from baseline) after enrollment, the investigator or qualified designee will determine if any change in participant management is needed. Any new clinically relevant finding will be reported as an adverse event (AE).

7.2 PARTICIPANT DISCONTINUATION/WITHDRAWAL FROM THE STUDY

Participants are free to withdraw from participation in the study at any time upon request. An investigator may discontinue or withdraw a participant from the study for the following reasons:

- Pregnancy
- Significant study intervention non-compliance
- If any clinical adverse event (AE), laboratory abnormality, or other medical condition or situation occurs such that continued participation in the study would not be in the best interest of the participant
- Disease progression which requires discontinuation of the study intervention
- If the participant meets an exclusion criterion (either newly developed or not previously recognized) that precludes further study participation

The reason for participant discontinuation or withdrawal from the study will be recorded. Subjects who sign the informed consent form and receive the study intervention, and subsequently withdraw, or are withdrawn or discontinued from the study, will be replaced.

Participants will not be financially responsible for damage to, or loss of, equipment loaned to participants by investigators during this study.

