6.1.2 DOSING AND ADMINISTRATION

Participants are assigned TENS devices and VR to be used as needed. Participants are also instructed to use VR at least three times a day. The dosage for both devices will not change throughout the study. Individuals assigned to remote monitoring will be continuously monitored and any action will be physician-initiated. Participants in the control group will receive standard of care and TENS unit.

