9.3 POPULATIONS FOR ANALYSES

All randomized participants will be included in the dataset (ITT).

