9.4.4 ACCOMODATING ADDITION OF TENS UNIT TO THE CONTROL ARM

An ITT analysis "Includes all randomized patients in the groups to which they were randomly assigned, regardless of their adherence with the entry criteria, regardless of the treatment they actually received, and regardless of subsequent withdrawal from treatment or deviation from the protocol."^{ref} Accordingly, we will follow the original analysis plan described above with regard to analyzing results by study-arm. In addition to the ITT analysis, however, we will conduct a sensitivity analysis by repeating the statistical procedures in a per-protocol fashion wherein the members of the control arm who did not receive a TENS unit will be dropped from the sample. Directions, magnitudes, and significance of treatment effects will be presented for both analyses.

Furthermore, because the TENS unit will appear in both study arms - and unevenly in the control arm – we recognize that an ITT analysis strictly *by* study-arm risks misidentifying the effect of treatment, while a per-protocol analysis risks introduction of bias. Therefore, we will conduct an additional linear mixed model regression analysis using a term for the TENS that captures the effect of the TENS separately from the effects of study-arm assignment. The model used to fit these data is as follows:

 $\hat{y}_{it} = \beta_0 + \beta_1 time_{it} + \beta_2 study_arm_{it} + \beta_3 TENS_{it} + e_{it}$

where time represents change in time from baseline, study_arm indicates status as a control or experimental participant (0= control and 1=experimental), *i* is the individual participant, and TENS indicates TENS unit usage (0= no TENS unit and 1=TENS unit). We can therefore write a regression equation describing each type of patient differentiated by the addition of the TENS unit to control conditions:

Treatment: $\hat{y}_{it} = \beta_0 + \beta_1 time_{it} + \beta_2 study_arm_{it} + \beta_3 TENS_{it} + e_{it}$

Control w/o TENS: $\hat{y}_{it} = \beta_0 + \beta_1 time_{it} + e_{it}$

Control w/ TENS:

 $\hat{y}_{it} = \beta_0 + \beta_1 time_{it} + \beta_3 TENS_{it} + e_{it}$

In this manner we isolate the term of interest (study_arm). Given we are only adding one term but 20 subjects, we are comfortable relying on the original power calculation.

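### Section 7.2 allows withdrawal and replacement for undefined intervention non-compliance, and no section keeps the PROMIS surveys going afterwards

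*Combined protocol and SAP*

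**What the plan says.** All references are to the combined protocol and SAP.

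- **7.2** lists reasons for which an investigator may withdraw a participant from the study. One is "Significant study intervention non-compliance". No threshold or definition is given. Participants who consented, received the intervention and "subsequently withdraw, or are withdrawn or discontinued from the study, will be replaced". The reason for withdrawal is recorded.
- **7.1** states: "Discontinuation from the use of the digital pain reduction kit does not mean discontinuation from the study". It adds that the remaining procedures should still be completed.
- **9.3** states: "All randomized participants will be included in the dataset (ITT". The ITT definition in **9.4.4** applies "regardless of subsequent withdrawal from treatment or deviation from the protocol".
- **6.3** names the monitoring sources: "Compliance to the protocol will be monitored using software for the VR modules and remote data uploads of survey logs". TENS use is self-reported by daily questionnaire (8.1) and has no usage target.
- **6.1.2** says "Participants are assigned TENS devices and VR to be used as needed" and then "Participants are also instructed to use VR at least three times a day". **4.3** calls the three daily sessions a recommendation that patients may adjust to their pain.
- **6.2** says that the trial is not blinded.
- **7.3** sets contact efforts for participants who miss the final visit, and leaves exit surveys to the participant's choice.

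**The concern.** A participant who stops using the headset fits both rules. Under 7.1 that person stays and is followed. Under 7.2 the investigator may end participation and recruit a replacement. Nothing says which rule governs, and non-compliance is hard to define for a device used as needed.

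The statistical cost is the outcome data after withdrawal. No section says that the weekly PROMIS surveys or the Day 60 assessment continue after a 7.2 withdrawal, and section 9 has no missing-data rule. Because 4.3 ties VR use to pain, low use may mark either a patient who gave up or one who recovered, so scores lost in this way may be related to outcome. Staff who know the allocation apply an undefined criterion, and they have better information on low use in the VR arm than in the control arm. The loss could therefore differ between arms and shift the comparison that randomisation is meant to protect.

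**Working it through.** **Does any section close the gap?** 7.1 covers stopping the kit, not leaving the study. 7.3 covers missed final visits and participants who cannot be reached. 6.1.1 keeps patients who decline coaching in the ITT population, but does not address device use. 9.3 keeps withdrawn participants in the dataset but cannot supply scores that were never collected. So the gap is real. It consists of missing later scores, not deleted participants.

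**Where would it matter?** Scores before withdrawal stay in the mixed model. The additional difference-in-differences analysis in 9.4.2 and 9.4.3 needs an end value, so it is the more exposed.

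**How large could it be?** The plan gives no figure for such withdrawals, so the inputs are partly assumed.

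- From the documents: T-score SD 10 and MCID 2 points (8.1); planned effect 0.6 SD = 0.6 × 10 = 6 points and a 25% withdrawal allowance (9.2); 75 per arm (6.2).
- Assumed: w, the share of the VR arm withdrawn for low device use, from 0% to 10%; d, mean change in retained minus withdrawn patients, from −6 to +6 points; no such withdrawals among controls; SD of change 10 or 7.

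With mean change m_r in retained and m_w in withdrawn patients, full follow-up gives (1 − w)·m_r + w·m_w. Losing the withdrawn gives m_r. The shift is therefore w × (m_r − m_w) = w × d.

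- 0.05 × 2 = 0.1; 0.05 × 6 = 0.3; 0.10 × 2 = 0.2; 0.10 × 6 = 0.6. Negative d reverses the sign.
- If a share p gave up and 1 − p improved, the shift is w × d × (2p − 1). With w = 10% and d = 6, p = 0.75 gives 0.3 and p = 0.5 gives 0.
- If controls are also withdrawn for low TENS use (share w_c, gap d_c), the shift is w × d − w_c × d_c, which is zero when the two terms are equal.
- Outside the assumed range, if the whole 25% allowance were VR-arm device withdrawals with d = 6, the shift would be 0.25 × 6 = 1.5 points. Nothing in the documents suggests this.

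**Type I error** with 75 v 75 after replacement and no true effect: SE = SD × √(2/75), which is 1.633 (SD 10) or 1.143 (SD 7). The two-sided rate is P(|Z + shift/SE| > 1.96).

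| Shift (points) | SD 10 | SD 7 |
|---|---|---|
| 0.2 | 5.2% | 5.4% |
| 0.3 | 5.4% | 5.8% |
| 0.6 | 6.6% | 8.2% |

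**Mixed model.** Keeping 75 at w = 10% means randomising 75/0.9 ≈ 83, so 8 are replaced. A simulation used 100 runs per setting, 83 v 75, the ten survey days of 1.3, no true difference, a random intercept, and a last score at Day 14 for those withdrawn. The assumed SDs were 8 between patients, 5 for slope and 4 residual. Shifts relative to full follow-up were:

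| d | Difference-in-differences | Time + arm | Time × arm |
|---|---|---|---|
| +6 | 0.60 | 0.22 | 0.57 |
| −6 | −0.58 | −0.23 | −0.57 |

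The time + arm form follows the equation in 9.4.4, whose TENS term is constant in this cohort. The plan does not specify a time-by-arm term.

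**Is replacement needed for power?** On the inputs in 9.2 (two-sided test assumed), n = 2 × (1.96 + 0.8416)²/0.6² = 43.6, so 44 per arm, or 44/0.75 ≈ 59 after 25% loss. With 75 per arm and 25% lost, 56.25 remain and power is Φ(0.6 × √(56.25/2) − 1.96) = Φ(1.22), about 89%. These inputs do not reproduce the 120 per arm and 245 in total stated in 9.2; that is a separate matter.

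**The case against.** The strongest reply is that little is at stake. Withdrawal under 7.2 is discretionary, and 7.1 can be read alongside it so that non-users are kept. The stated response to low device adherence in 6.1.1 is a contact from support staff. The only withdrawals that the documents report, in the summary of changes for 9.2, were for low survey compliance. Those patients were already not returning scores, so withdrawing them adds little missingness. Reaching 0.6 points takes a gap equal to the full planned effect, every withdrawal in the same direction, and the additional analysis instead of the mixed model. All of this stands, and it limits the weight of the point. It does not remove the conflict between 7.1 and 7.2 or supply a rule for follow-up after withdrawal.

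A reader might infer two stronger claims that the text does not support.

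- *That 7.2 breaches ITT by removing people from the analysis.* It does not. 9.3 keeps all randomised participants, and replacement is a recruitment rule. The ITT aim is weakened only because later outcomes go uncollected.
- *That the rule reaches only the VR arm.* It reaches both. Survey logs count as compliance in 6.3, and TENS is a study device that current controls receive and report on daily. The arms differ in how easily low use is detected, not in whether the rule applies.

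The mixed dose wording in 4.3 and 6.1.2 can be read together: three sessions as a target, adjustable to pain. It calls for clarification at most.

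**Conclusion.** The concern holds as a modest, correctable weakness in conduct. The plan allows discretionary, undefined withdrawal with replacement, in tension with 7.1, and makes no provision for outcome collection afterwards. The resulting loss could be uneven between arms and related to outcome.

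Its size is unknown. For w up to 10% and d within ±6 points, the difference-in-differences shift lies between −0.6 and +0.6 points, against an MCID of 2, and type I error is at most 8.2%. These figures rest on assumed w, d and SDs. The direction is also unknown: losing patients who gave up favours the kit, and losing those who improved counts against it. No withdrawal for low VR use is reported, and the shift is zero if the rule is never used for device use. The documents therefore do not show that the trial's result is biased.

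**What to change.** 1. Delete the non-compliance ground from 7.2. State in 7.1 that low or no use of VR, TENS or coaching may lead to support contact or to stopping the device, but not to leaving the study.
2. Add to 7.2 that weekly PROMIS surveys and the Day 60 assessment continue after any investigator-initiated discontinuation, unless the participant withdraws consent. This must cover every ground, including adverse events and disease progression. The latter is clearly outcome-related and has the same gap.
3. State that all randomised participants are analysed in their assigned arm, and that any added enrollees are additional randomised participants, not substitutes.
4. Report withdrawals by arm and reason, separating device from survey non-compliance. Add a simple sensitivity analysis of the baseline-to-end comparison. For example, predict missing end values from the mixed model, then shift them by −6, −2, +2 and +6 points.

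As a clarification only, use one sentence in 4.3 and 6.1.2 that makes three VR sessions a day a recommended target, adjustable to pain. An adherence cut-off is not needed.

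The cost is one IRB amendment and a little more analysis work. The surveys are already scheduled in 1.3, and 7.2 already records withdrawal reasons. Deleting the ground also ends withdrawal for low survey return in both arms, while 7.3 still covers participants who cannot be reached. At w = 10%, about 8 fewer replacements would be recruited.

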7.3 LOST TO FOLLOW-UP

A participant will be considered lost to follow-up if he or she fails to comply to weekly surveys, misses exit appointment, and is unable to be contacted by the study site staff.

The following actions must be taken if a participant fails to return to the clinic for the final study visit:

- The site will attempt to contact the participant and reschedule the exit appointment and counsel the participant on the importance of maintaining the assigned visit to return equipment and debrief (whether or not the participant chooses to complete exit surveys).
- Before a participant is deemed lost to follow-up, the investigator or designee will make every effort to regain contact with the participant (where possible, 3 telephone calls and, if necessary, a certified letter to the participant's last known mailing address or local equivalent methods). These contact attempts should be documented in the participant's study file.
- Should the participant continue to be unreachable, he or she will be considered to have withdrawn from the study with a primary reason of lost to follow-up.

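### Section 7.2 allows withdrawal from the study, not only from the device, for disease progression, so end scores related to the outcome can be lost

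*Combined protocol and SAP*

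**What the plan says.** Section 7.1 sets the general rule: "Discontinuation from the use of the digital pain reduction kit does not mean discontinuation from the study", and the remaining procedures should still be completed.

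Section 7.2 sets a separate rule for leaving the study: "An investigator may discontinue or withdraw a participant from the study for the following reasons". One listed reason is "Disease progression which requires discontinuation of the study intervention". Another, broader item covers any "other medical condition or situation occurs such that continued participation in the study would not be in the best interest of the participant". Two consequences follow. First, "The reason for participant discontinuation or withdrawal from the study will be recorded". Second, participants who consented and received the study intervention and who then withdraw, "or are withdrawn or discontinued from the study, will be replaced". Section 7.2 says nothing about outcome data after withdrawal.

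Section 7.3 does contain recovery steps ("The site will attempt to contact the participant and reschedule the exit appointment", followed by telephone calls and a letter), but they are for participants who fail to return for the final visit.

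Section 6.2 states that the trial is not blinded. Sections 9.3 and 9.4.4 define the analysis set as all randomized participants in their assigned groups. Section 9.4.2 plans linear mixed models with random intercepts, together with a comparison of change from baseline to the end of the intervention.

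**The concern.** The progression item describes an event that calls for stopping a device, yet the consequence it permits is leaving the study. The same clinical event can therefore fall under 7.1, where follow-up continues, or under 7.2, where no further follow-up is stated. The choice rests with an investigator who can know the assigned arm.

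Worsening disease is plausibly related to physical function, the primary outcome, so the scores lost this way are unlikely to be a random subset. A participant withdrawn while worse has no end score and drops out of the baseline-to-end comparison. If this happens more often in one arm, the estimate shifts in favour of that arm, whichever it is. The mixed model keeps the earlier weekly scores and is affected less. It is not immune: PROMIS is collected weekly with a 7-day recall (sections 1.3 and 8.1), so worsening that leads to withdrawal between two surveys may never be scored. Section 9 gives no method for missing data.

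**Working it through.** **The texts side by side.** Under 7.1 a person who stops the kit stays and completes the remaining procedures. Under 7.2 a person whose progression requires the intervention to stop may be withdrawn from the study, with the reason recorded and a replacement enrolled. Section 7.3 does not fill the gap, because its steps start from a missed final visit. Sections 9.3 and 9.4.4 decide who is analysed, not what is collected.

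**Inputs.** The plan gives no rate for this ground and no bias figure to reproduce. From the documents: 75 per arm (4.1, 6.2); PROMIS SD 10 and MCID 2 points (8.1); assessments on Day 1, weekly from Day 7 to Day 56, and Day 60 (1.3). Assumed: no true effect; k = 2, 4 or 8 excess withdrawals in one arm; unseen change d = 10 points worse than that of participants who stay (range 5 to 15); baseline-to-end correlation r of 0.5 to 0.7.

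**Baseline-to-end contrast.** If a share f of an arm is withdrawn and their mean change is d points worse than the completers', the completer mean exceeds the full-arm mean by exactly f × d. At d = 10:

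- 2/75 × 10 = 0.27
- 4/75 × 10 = 0.53
- 8/75 × 10 = 1.07

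The extremes are 2/75 × 5 = 0.13 and 8/75 × 15 = 1.60. The MCID is reached at d = 10 only when 15/75 × 10 = 2.0, that is, at 20% of the arm.

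**Chance of a false result favouring the arm with more withdrawals.** This is 1 − Φ(1.96 − bias/SE), with SD of change 10√(2(1 − r)) and SE = SD × √(1/(75 − k) + 1/75). For k = 8 and r = 0.7: SD = 7.75, SE = 7.75 × √(1/67 + 1/75) = 1.30, bias/SE = 1.07/1.30 = 0.82, giving 12.7%. The nominal value is 2.5%.

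**Random-intercept model.** This was simulated with 2,000 trials per setting, SD 10, a 4-point mean recovery and two assumed covariance structures. In each arm k participants fall by d from a random post-baseline visit onward, and only one arm's are withdrawn. The model has linear time and a study-arm main effect, following 9.4.4; the TENS term drops out because all 150 simulated participants have TENS.

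| k of 75, d = 10 | Baseline-to-end bias | False positive, r = 0.5 | False positive, r = 0.7 | Mixed-model bias, first worsened score recorded | Mixed-model bias, not recorded |
|---|---|---|---|---|---|
| 2 | 0.27 | 3.6% | 4.0% | 0.08 | 0.13 |
| 4 | 0.53 | 5.1% | 6.1% | 0.16 | 0.26 |
| 8 | 1.07 | 9.3% | 12.7% | 0.30–0.31 | 0.52 |

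- A second, independent simulation agreed with the mixed-model biases to within about 0.01 point.
- Across d = 5 to 15 the mixed-model bias runs from 0.04 to 0.46 (recorded) and from 0.07 to 0.78 (not recorded).
- Its false-positive rates at d = 10 are 2.5–3.5%, 3–4.4% and 3.5–5.5%, with a Monte Carlo standard error of about 0.4 percentage points.
- Adding baseline PROMIS, a covariate listed in 9.1, changes little: at most 0.33 (recorded) or 0.58 (not recorded) at d = 10.

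**Direction.** Withdrawing only controls (k = 8, d = 10) reverses the sign: −0.30 or −0.52 in the mixed model, and −0.92 to −1.07 for baseline-to-end. Withdrawing the same number of similar patients in both arms gives at most 0.014 points in absolute value.

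**The case against.** The strongest reply is that the clause will rarely operate. Progression must require stopping the intervention, yet VR and TENS are as-needed devices meant for flares of pain (4.3, 6.1.1), so worsening is a reason to use them. The same list mentions laboratory abnormalities although the schedule has no laboratory test, which suggests generic wording. The clause is also permissive, and 7.1 already points the right way. This stands as far as frequency goes. It does not remove the conflict: 7.1 governs stopping the kit, and nothing in 7.2 says that 7.1 prevails.

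Bias also needs enough such withdrawals, an imbalance between arms, and much worse unseen change. The documents show none of these. Controls have TENS too, so either arm could lose more. This stands. Eight excess withdrawals would be 8/75 = 11% of an arm on one narrow ground. The 15 needed to reach the MCID compare with about 19 per arm (0.25 × 75) from all causes at the 25% withdrawal rate assumed in 9.2. Counting both tails, the error for the baseline-to-end contrast is only 5.3–5.5% at k = 2 and 6.2–7.0% at k = 4, against 5%.

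The simulated model is itself an assumption. Section 9.4.2 does not list arm and time terms, the 24 controls without TENS are left out, and the fall is taken to persist to Day 60. This too stands, and the mixed-model figures should be read as orders of magnitude.

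Finally, intention-to-treat already retains replaced participants, and the only withdrawal cause the documents report, low survey compliance, is a different matter. Both points are correct, but neither recovers an end score lost through the progression or medical-condition items.

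**Conclusion.** The concern holds, as an improvement that could be made rather than a serious flaw. Section 7.2 permits an unblinded investigator to take a participant out of the study for a reason related to the primary outcome. It states no later outcome collection, and intention-to-treat cannot repair that.

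The likely size is small. For 2 to 8 excess withdrawals of 75 and an unseen change 10 points worse, the bias is 0.27 to 1.07 points in the baseline-to-end contrast and 0.08 to 0.52 points in the random-intercept model. All of these are below the 2-point MCID. The upper figures need an excess that fits poorly with so narrow a ground. The direction is unknown, and balanced withdrawal of similar patients gives a bias of about zero. The textual finding is firm; every number rests on assumed rates, severity and correlation.

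**What to change.** Amend section 7.2 in three respects.

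- Move disease progression out of the study-withdrawal list and treat it as a reason to stop the device only, under 7.1.
- State that a participant whose intervention the investigator stops for progression or another medical reason continues the scheduled weekly PROMIS surveys and the Day 60 assessments, unless consent is withdrawn or continued participation is unsafe. Covering other medical reasons matters, because the broader item in 7.2 can otherwise remove the same people.
- State that a replacement is an additional randomized participant and does not displace the original from the intention-to-treat analysis. This largely repeats 9.3 and 9.4.4, but it settles what replacement means.

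The clinical decision to stop a device is unchanged. The cost is wording in an IRB-approved amendment. No new instrument is needed, since the remote weekly surveys and Day 60 assessments are already scheduled for every participant. The change does not address withdrawal for non-compliance, which would need its own rule.

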2.3.1 KNOWN POTENTIAL RISKS

Short-term risks associated with the study may include minor psychological distress from questionnaires regarding health and employment status, acute virtual reality discomfort (e.g., headache, vertigo, nausea), and minor side effects from transcutaneous electrical nerve stimulation (e.g., muscle twitching, muscle soreness, skin irritation). There are no anticipated long-term risks from participating in this study.

Participants may elect to receive standard of care in lieu of participation in the study.

There are some risks associated with the electronic collection and transmission of protected health information for the purpose of research. Unanticipated breaches of data may result in exposure of confidential information to individuals outside of study staff.

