5.2 EXCLUSION CRITERIA

An individual who meets any of the following criteria will be excluded from participation in this study:

- 1. Unable to understand the goals of the study due to cognitive difficulty
- 2. Pregnant (contraindication for TENS unit)
- 3. Use of a cardiac pacemaker, implanted defibrillator, or other implanted metallic or electronic device or high frequency surgical equipment. (contraindication for TENS units)
- 4. Current diagnosis of epilepsy, dementia, or other neurological disease that may prevent use of VR hardware or software
- 5. Hypersensitivity to flashing light or motion
- 6. Injury to the eyes, face, neck, or arms that prevents comfortable use of VR hardware or software, or safe use of other study hardware (e.g., open sores, wounds, or skin rash on face)

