6 STUDY INTERVENTION

6.1 STUDY INTERVENTION(S) ADMINISTRATION

6.1.1 STUDY INTERVENTION DESCRIPTION

Study Intervention: Digital Pain Reduction Kit

The study intervention will include evidence-based digital devices that offer non- pharmacological solutions to managing pain. Patients in the intervention group will receive access to two devices: (1) Oculus Go headset or PICO G2 headset with preloaded therapeutic visualization software developed by appliedVR; (2) Aleve® Direct Therapy TENS Device. Study staff will monitor patient progress remotely and provide guided support and coaching. The sections, below, describe the components of the intervention.

Smartphone, VR Headset, and Software

To care for the whole patient, clinicians must consider not only the physical impact of illness, but also the psychosocial impact. However, the dynamic nature of clinical medicine, coupled with limited time to spend with individual patients, pose challenges to offering holistic care for patients with pain.

Treatment of pain is often focused on pharmacological management which can yield inconsistent and sub-optimal pain control.[2] However, extensive data reveal that adjunctive non-pharmacological techniques, such as cognitive behavioral therapy and relaxation techniques, can modify cognitions and behaviors that influence the perception of pain.[3] VR technology provides an immersive, multisensory, and three-dimensional (3D) environment that enables users to have modified experiences of reality by creating a sense of "presence".[4 5] To date, VR has been used in numerous clinical settings to help treat anxiety disorders, control pain, support physical rehabilitation, and distract patients during wound care.[4-12] For example, VR coupled with medication is effective in decreasing pain during bandage changes for severe burns.[6 10 13 14] Similarly, VR reduces pain and provides positive distraction during routine procedures, such as intravenous line placements[9] and dental procedures.[7 15] Other studies reveal that VR helps manage chronic pain conditions such as complex regional pain syndrome[16] and chronic neck pain.[17] Our own research shows that VR can reduce pain by an average of 24% among hospitalized patients with a wide

range of somatic and visceral pain. By stimulating the visual, auditory, and proprioception senses, VR acts as a distraction to limit the user's processing of nociceptive stimuli.[5]

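### Section 7.2 lets a randomised patient be withdrawn from the study and replaced for an exclusion criterion found later; outcome collection is not continued, and the loss can differ by arm

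*Combined protocol and SAP*

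**What the plan says.** **Withdrawal and replacement (Section 7.2).** The list opens with "An investigator may discontinue or withdraw a participant from the study for the following reasons", and one of the reasons is "If the participant meets an exclusion criterion (either newly developed or not previously recognized) that precludes further study participation". Those who consent and "receive the study intervention, and subsequently withdraw, or are withdrawn or discontinued from the study, will be replaced". The reason for each withdrawal is to be recorded.

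**Stopping the kit (Section 7.1).** A patient who stops using the kit remains in the study and completes the remaining procedures.

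**Analysis set (Sections 9.3 and 9.4.4).** All randomised participants are in the ITT dataset. The ITT definition that the plan adopts keeps patients "regardless of their adherence with the entry criteria, regardless of the treatment they actually received". The only stated removal is of controls without a TENS unit, in a sensitivity analysis.

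**Exclusion criteria (Section 5.2).** Criterion 5 is "Hypersensitivity to flashing light or motion". Criterion 4 covers neurological disease that may prevent VR use. Criterion 6 covers injury that prevents comfortable VR use or safe use of other study hardware. Criteria 1 to 3 concern cognition, pregnancy and implanted devices.

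**Arms and blinding.** Controls receive TENS but no VR (Section 1.1). There is no blinding, and randomisation continues until each group has 75 enrollees (Section 6.2).

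**Analysis (Section 9.4.2).** The primary analysis is a linear mixed model with random intercepts, plus a difference-in-differences comparison of baseline with the end of the intervention.

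**The concern.** Membership of the ITT set does not supply outcomes. Once a patient is withdrawn from the study, the documents provide for no further surveys, and they name no method for missing data. The analysis sections promise to keep a patient whom the conduct section allows to leave follow-up because of an entry criterion.

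The loss need not be equal between arms. A tendency to react to light or motion that was missed at screening would most naturally show itself in a headset, and only the kit arm wears one. The decision is discretionary and is taken with the arm known. A control with the same trait has little reason to be identified, and the trait would hardly preclude a control's participation.

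Replacement adds a second difficulty. Section 6.1.1 opens with "Study Intervention: Digital Pain Reduction Kit". Read literally with that label, the replacement sentence in Section 7.2 may cover kit patients only. The documents do not say whether a replacement is newly randomised or takes the vacated arm, or whether the 75 includes the patients replaced.

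At stake is arm-dependent missing data on a self-reported primary outcome in an open trial.

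**Working it through.** **1. The sections side by side, for a kit patient found after randomisation to meet criterion 5**

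- Section 7.1: if only the device is stopped, follow-up continues.
- Section 7.2: the investigator may instead end study participation, and the patient is replaced.
- Sections 9.3 and 9.4.4: the patient stays in the ITT set in either case.
- Section 9.4.2: the mixed model can use weekly scores recorded before withdrawal. The baseline-to-end comparison has no end value for this patient.

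Nothing states which of 7.1 and 7.2 governs, or that outcomes continue under 7.2.

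**2. Which criteria can depend on arm**

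- Criterion 5: plausibly needs headset exposure to emerge.
- Criterion 4: requires a current diagnosis, which medical history can reveal in either arm; partly arm-dependent at most.
- Criterion 6: usually visible at screening, and also covers other hardware, including the TENS unit; partly arm-dependent at most.
- Criteria 1 to 3: not arm-dependent under the current design.

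**3. Size, by assumption**

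The plan gives no figure for this. Let p be the share of the kit arm leaving by this route, and g the number of T-points by which they would have scored below those who stay. If the stayers' mean is S, the full-arm mean is (1 − p)S + p(S − g) = S − pg. With no data from leavers, the kit mean is therefore too high by p × g. Replacements who meet the same filter restore the number but not the composition.

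Inputs from the documents: SD 10 and MCID 2 (Section 8.1), and 75 per arm (Section 6.2). Both p and g are assumptions. The standard error of the difference is 10 × √(2/75) = 1.63 points. The last column is the two-sided type I error at nominal 5%.

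| p (patients of 75) | g | bias = p × g | type I error |
|---|---|---|---|
| 2% (1.5) | 2 | 0.04 | 5.0% |
| 2% (1.5) | 6 | 0.12 | 5.1% |
| 5% (3.75) | 2 | 0.10 | 5.0% |
| 5% (3.75) | 6 | 0.30 | 5.4% |
| 10% (7.5) | 2 | 0.20 | 5.2% |
| 10% (7.5) | 6 | 0.60 | 6.6% |
| 20% (15) | 2 | 0.40 | 5.7% |
| 20% (15) | 6 | 1.20 | 11.4% |

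The top rows of p are demanding: 20% by this one route would use 20/25 = 80% of the 25% allowance for all withdrawals in Section 9.2. If g were negative, the bias would reverse.

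**4. Whether replacement is needed for power**

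Section 9.2 assumes 0.6 SD, 80% power, level 0.05 (taken as two-sided) and 25% withdrawal. Then n = 2(1.96 + 0.84)² / 0.6² = 43.6, so 44 per arm; 44/0.75 = 58.7, so 59 per arm, or 118 in total. The stated figures of about 120 per arm and 245 in total are not reproduced, which is a separate matter. With 75 per arm, power for 0.6 SD is 95.7%. With 75 × 0.75 ≈ 56 evaluable per arm it is 88.8%. On the plan's own inputs, 80% power does not depend on replacement.

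**The case against.** The strongest reply is that Section 7.2 governs participation, not the analysis set. A patient can be withdrawn under 7.2 and still be analysed as randomised with whatever data exist. That stands. A reader might infer that 7.2 removes these patients from ITT and so breaks the rule that the plan quotes; the documents do not say so, and Sections 9.3 and 9.4.4 say the opposite.

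Second, Section 7.1 already addresses a patient who merely stops using the headset, and the 7.2 clause is discretionary and limited to criteria that preclude participation. Headset nausea does not obviously preclude a remote survey, and the adverse-event reason in the same list is its more natural home. This also stands, and it narrows the route. It does not close it, because nothing tells the investigator to prefer 7.1.

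Third, a reader might infer that the rule strips poor VR tolerators out of the kit arm and so favours the kit. The documents do not establish this. Only criterion 5 clearly depends on headset exposure, no rate is given, and nothing shows that motion-sensitive patients have worse physical function.

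Fourth, the non-compliance and adverse-event reasons may be larger routes to the same imbalance. That may be so, but amending them alone would leave this one in place.

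Fifth, replacements do not themselves bias the result if the patients they follow remain in ITT, and recorded reasons allow reporting by arm. That is right, provided the plan states that replacements are additional and that the counts will be reported. It states neither.

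**Conclusion.** The point holds as a gap between conduct and analysis. The plan keeps these patients in the ITT set but lets their follow-up end on an entry criterion, without continued outcome collection or a missing-data method. The loss can differ by arm because VR is used in one arm only and the decision is unblinded. The baseline-to-end comparison is the more exposed of the two analyses.

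The size and direction of any bias cannot be determined from the documents. Under the assumed ranges (p = 2-20%, g = 2-6 points, no data from leavers) it runs from 0.04 to 1.2 T-points. It is at most 0.3 points when p is 2-5%. Scores before withdrawal would probably reduce these figures in the mixed model, fully only if the loss is ignorable given those scores.

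**What to change.** Reconcile Sections 7.1, 7.2, 9.3 and 9.4.4 so that, when a patient is found after randomisation to meet an exclusion criterion:

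- whether device use continues remains a clinical decision, on which this point takes no position;
- weekly PROMIS and Day 60 outcomes continue in both arms, unless the patient withdraws consent or can no longer self-report;
- the patient stays in the randomised arm in the ITT analysis;
- the 75 per arm counts randomised patients, and any replacement is an additional randomised patient who does not stand in for the one withdrawn;
- the number of such cases is reported by arm and by criterion.

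The cost is protocol wording. The surveys are already remote and prompted automatically (Section 8.1). The downside is that a few patients with little kit exposure stay in follow-up, which may slightly dilute the estimated effect.
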